## **Statistical Analysis Plan**

**Specific Aim 1:** Repeated measures analysis of variance (ANOVA) will be used to assess differences between intervention and control groups on outcomes variables over time. Post-hoc analysis will be based on Fisher's least significant difference procedure for pairwise comparisons. Baseline comparisons between those who dropped out and those who completed all three waves of data collection will be determined using two-sample t-tests or chi-square tests, and the rate of retention will be compared between the two treatment arms using the chi-square test of association to assess whether differential drop-out occurred.

**Specific Aim 2:** Kaplan-Myer survival analysis with a logrank test will be used to make an overall comparison between time to rehospitalization or death event between intervention and control groups. Cox proportional hazards model will be used to estimate the hazard ratio of intervention effect on the prediction of the end-point of rehospitalization or death compared to usual care group, while controlling potential compounding factors.

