A two-group, randomized controlled design will be used to determine the effect of Family SWaP on sodium intake of patients with HF and family caregivers (Figure 1). Dyads will be randomly assigned to intervention or usual care group using a stratified randomization strategy after we determine patients' adherence level to SRD at baseline. Because adherence level at the baseline may affect outcomes, stratification is needed to insure similar sample characteristics between Family SWaP and usual care groups. Non-adherence will be defined as a 24-hour urinary sodium excretion greater than 3000 mg. The 3000 mg 24-hour urinary sodium excretion cut point was chosen because it is the upper limit of sodium intake recommended for patients with HF. The intervention will be delivered to both adherent and non-adherent patients because it has not known whether the intervention delivered to a dyad can maximize their adherence behavior or promote long-term adherence behavior. The intervention will be delivered 16 weeks (6 weekly 45 minutes sessions and 5 bi-weekly 20 minutes sessions).using video conferencing technology via digital device (i.e., ipad). Post-intervention effects will be assessed at 4 and 12 months to identify short- term and long-term post-intervention. We will collect hospitalization information up to 12 months by phone follow up. Dependent variables include adherence to the SRD, symptom distress, knowledge of SRD, perceived control, perceived social support, quality of life, and caregiving burden (caregiver only), symptom distress (patient only), and rehospitalization (patient only). We will also collect 4 variables to evaluate salt taste: salt food preference, sensory density, and diet quality. Qualitative data regarding salt taste preference and family experiences.

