A total of 300 patient-caregiver dyads (i.e., 600 individuals; see sample size justification in data analysis section) will be randomized into intervention and usual care groups. Eligible patients will have (1) have a diagnosis of chronic heart failure with either preserved or non- preserved ejection fraction (2) be able to speak and write English, (3) have a phone in home and (4) without cognitive impairment of dementia and Alzheimer. Patients will be excluded if they have a co- existing terminal illness, or have a dietary prescription at odds with following a 2-3 gram sodium diet (e.g., clinician does not support use of a SRD). Patients without dedicated caregivers are excluded in this study. Improving outcomes of patients without caregivers are important to study, but it is not appropriate to include them in this study. After this study demonstrate effect of gradual adaptation strategy, it will be important to test the effect on patients without caregivers by providing support from nurses. A family member is eligible if he/she is: (1) a primary caregiver identified by a patient; (2) the spouse, committed partner, or family member living with the HF patient; (3) able to speak and understand English; (4) without cognitive impairment of dementia and Alzheimer. Despite the fact that HF is equally distributed between the genders, the representation of women in many studies of HF has been low. We plan to enroll 50% female patients. The population of HF patients at the University of Kentucky Medical Center (UKMC) is sufficient and approximately 50% are women, so we do not anticipate difficulty in obtaining an adequate sample of women and men with HF for this study. Based on our dyadic study, we expected at least 10% more female caregivers than male caregivers. This is consistent with the common observation that more females take on the caregiver role than males. Based on national estimates and University of Kentucky Chandler Hospital (UKCH) discharge data, planned enrollment in this study is 80% Caucasian and 20% African American.

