After eligible patient-caregiver dyads sign the consent forms, they will participant in this study. Baseline data will be collected during a home visit. At the baseline assessment, they will fill out questionnaires using the RedCap system and collect 24-hour urine specimens. Urine containers, collection devices (urinals for men and toilet "hats" for women) and written instructions will be provided. The research assistant will interview participants to obtain demographic characteristics and to confirm their comorbidities. Information about demographics and comorbidities will be obtained using a structured questionnaire in interview. A research assistant and the dyads will set up the starting day of urine collection within 3 days of completion of questionnaires and pick up dyad's urine specimens in the dyad's home and deliver University of Kentucky Chandler Hospital Laboratory to determine 24-hour urinary sodium excretion level. Additional data collection for qualitative data, and diet quality will be also collected by home visiting. The medical chart will be reviewed to confirm only patients' comorbidities. After patients are categorized as adherent or non- adherent using 3000mg urine sodium cut point, the dyads will be randomly assigned to the Family SWaP intervention or usual care group using stratified randomization. Caregivers' adherence level at baseline will not be used in randomization but will be used to compare adherence at follow up. Dyads in the Family SWaP intervention will participate in a 16-week intervention delivered by the interventionist. The usual care patients will receive the standard medical and nursing care for HF patients provided at the clinics from which they were recruited. The usual care dyads will participate in the same data collection procedures as dyads in the intervention group. Follow-up data collection will be conducted 4 and 12 months after the intervention group completes the 16 week intervention to evaluate short and long term effects. At each follow-up, patient-caregiver dyads will complete the same questionnaires as baseline. Self-report of all hospitalization events will be collected from patients/family caregiver via monthly phone calls and a hospitalization logbook kept by the dyad for 12months. The medical record and administrative database will be queried to confirm rehospitalizations by the research nurse who will be blinded to the study group assignment. Data from the optional recorded interviews will be transcribed by a HIPAA compliant third party transcription service (REV).

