There is no monetary incentive to compensate for their time during 12 months. However, each dyad (patients and their family caregiver dyad) who participant in this study will receive an iPad per family at the beginning of the study. If any one of the dyad members withdraws the study before three assessments complete, we consider patient-caregiver dyad as a unit of the study will end the study and they should return the iPad that will be given during the study. When two dyad members complete all three assessments during 12 months study, the dyad will keep the iPad. Free data plan will be provided for only dyads that don't have home Wi-Fi access during the study (12 months).

**Costs to Subjects:** Describe any costs for care associated with research (including a breakdown of standard of care procedures versus research procedures), costs of test drugs or devices, and research procedure costs that are the subject's responsibility as a consequence of participating in the research. Describe any offer for reimbursement of costs by the sponsor for research related injury care.

There will be no additional costs to the participants and no personal travel costs to the research site.

**Data and Safety Monitoring:** The IRB requires review and approval of data and safety monitoring plans for greater than minimal risk research, clinical research, or NIH-funded/FDA-regulated clinical investigations.

If you are conducting greater than minimal risk research, clinical research, or your clinical investigation is NIH-funded/FDA-regulated, describe your Data and Safety Monitoring Plan (DSMP). [Click here for additional guidance on developing a Data and Safety Monitoring Plan.](#)

If this is a *non-sponsored investigator-initiated* protocol considered greater than minimal risk research, clinical research, or your clinical investigation is FDA-regulated, *and* if you are planning on using a Data and Safety Monitoring Board (DSMB) as part of your

DSMP, [click here for additional guidance](#) for information to include with your IRB application.

If relying on an independent agent or committee for DSMB services, it is the PI's responsibility to establish the services with the agent or committee. Please be reminded that the PI must submit DSMB reports to the IRB via modification or continuing review. 

We have developed a detailed Data Safety Monitoring Plan that includes the following elements.

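### Fisher's LSD with one pooled repeated measures error could test the long-term change at about 6-10% where 5% is intended, if within-person correlation falls with time; use contrasts with their own standard errors

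*Combined protocol and SAP*

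**What the plan says.** The Statistical Analysis Plan, Specific Aim 1, sets the model in one sentence: "Repeated measures analysis of variance (ANOVA) will be used to assess differences between intervention and control groups on outcomes variables over time". The next sentence adds: "Post-hoc analysis will be based on Fisher's least significant difference procedure for pairwise comparisons". The section does not give the error term for those comparisons, a sphericity check or correction, a covariance structure, the pairs to be compared, or alpha. It also does not say whether the omnibus F must be significant first. No within-person correlation appears anywhere in the document.

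There are three waves: the same section refers to "those who completed all three waves of data collection". Their timing is less clear. Research Procedures says: "Follow-up data collection will be conducted 4 and 12 months after the intervention group completes the 16 week intervention". Sixteen weeks is about 4 months, which puts the waves at about 0, 4 + 4 = 8 and 4 + 12 = 16 months. Study Design says only "Post-intervention effects will be assessed at 4 and 12 months", and Payment has "When two dyad members complete all three assessments during 12 months study"; both fit waves at 0, 4 and 12 months. These statements need to be reconciled. The check below covers both schedules.

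Study Design makes short-term and long-term effects the purpose of the two follow-ups, and Study Population gives the size as "A total of 300 patient-caregiver dyads".

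**The concern.** In its standard form, LSD takes the error mean square of the ANOVA and uses it for every pair. After a repeated measures ANOVA this is right only if the change between any two waves has the same variance, which is the sphericity condition. Repeated measurements on a person usually become less alike as the interval grows. If that happens here, the change from baseline to the last wave has the largest variance of the three changes, and an error averaged over all of them is too small for it.

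The long-term change is one of the two results the trial is designed to deliver. Its standard error would be too small and its interval too narrow. On equally spaced waves the short-term change would have the opposite fault. A statement that an effect lasted, or faded, would then rest on two tests run at different actual levels.

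**Working it through.** **Inputs.** From the documents: two randomised arms, three waves, 300 dyads. Assumed: 150 per arm (the ratio is not stated), two-sided alpha of 0.05, equal variance s² at each wave, and the correlations shown. The plan has no figure of its own to reproduce on this point.

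**Formula.** The pooled within-subject error is s²(1 − mean ρ), averaging over the three pairs of waves. The true variance of a change from wave i to wave j is 2s²(1 − ρ_ij), while the pooled error implies 2s²(1 − mean ρ). So

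- k = (1 − ρ_ij) / (1 − mean ρ)
- actual level = 2[1 − Φ(1.96/√k)]

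The same k applies to the between-arm difference in change, because both variances scale alike with the number per arm.

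**Worked case**, correlations 0.6/0.6/0.4 (waves 1-2, 2-3, 1-3): mean ρ = 1.6/3 = 0.533. For the long-term change k = 0.6/0.467 = 1.286, 1.96/√1.286 = 1.73, level 8.4%. For an adjacent-wave change k = 0.4/0.467 = 0.857, level 3.4%.

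| Assumed correlations (1-2, 2-3, 1-3) | k, long-term | Level, long-term | Level, adjacent waves |
|---|---|---|---|
| equal | 1.000 | 5.0% | 5.0% |
| 0.5, 0.5, 0.45 | 1.065 | 5.8% | 4.6% |
| 0.6, 0.6, 0.5 | 1.154 | 6.8% | 4.1% |
| 0.7, 0.7, 0.6 | 1.200 | 7.4% | 3.9% |
| 0.3, 0.3, 0.09 | 1.182 | 7.1% | 4.0% |
| 0.6, 0.6, 0.4 | 1.286 | 8.4% | 3.4% |
| 0.8, 0.8, 0.64 | 1.421 | 10.0% | 2.7% |
| 0.9, 0.9, 0.81 | 1.462 | 10.5% | 2.5% |

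The rows in which the third correlation is the square of the first are AR(1) decay on equally spaced waves (0, 8, 16 months).

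**Other schedule.** With waves at 0, 4 and 12 months and exponential decay, 4-month correlations of 0.5 to 0.9 give 7.8% to 10.4% for the long-term change. The baseline-to-4-month change falls to 2.0% to 0.7%, and the 4-to-12-month change stays near 5% (5.7% to 5.2%). The long-term result therefore does not depend on which schedule is meant.

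**Simulation.** 150 per arm, AR(1) with adjacent correlation 0.5 to 0.8, 20,000 trials per setting (Monte Carlo standard error at 5%: √(0.05 × 0.95/20,000) = 0.15 percentage points). Rejection rates where the long-term difference is truly zero:

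| Test | Rate |
|---|---|
| Long-term change, pooled error, no gate | 8.6-10.0% |
| Same, after significant uncorrected F, no effect at any wave | 4.4-5.2% |
| Same, after significant Greenhouse-Geisser F, no effect at any wave | 4.2-4.6% |
| Same, gated by either F, real effect of 0.4 SD at wave 2 only | 8.6-10.0% |
| Long-term change, its own standard error | 5.0-5.2% |
| Arms compared at wave 3 only | 4.7-4.8% |
| Omnibus group-by-time F, uncorrected, no effect | 5.4-5.8% |

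In the fading-effect row the omnibus F is significant in 95% or more of trials, so the gate is almost always open and gives no protection.

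**The case against.** A reader might infer that the plan will test its long-term effect at 8-10%. The documents do not support that, for five reasons.

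- **Error term.** The plan does not say the error is pooled. Pooling is the standard meaning of LSD, but it can be run with each contrast's own standard error, and the level is then about 5%.
- **Size.** No correlation is given. The 8-10% range needs near-AR(1) decay with adjacent correlations of about 0.5 to 0.8; milder decay gives about 6-7%. Outcomes measured by one 24-hour urine collection per wave could well have low, flat correlations.
- **Gate.** Classical LSD follows a significant omnibus F, and the plan calls the comparisons post-hoc. With that gate and no effect at any wave, the long-term contrast holds about 4-5%.
- **Pairs.** The comparisons may be between arms at one wave, which stay near 5% under equal variances.
- **Alpha and unseen text.** The 5% is itself assumed. Study Population also points to a data analysis section that is not in the available text and might say more.

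All five stand as limits on the size of the problem, but they do not remove it. The gate fails where a true short-term benefit has gone by the last wave, which is the pattern a short-term and long-term design has to recognise. A gate also leaves the standard error, and so the interval, uncorrected. And because the wording permits both forms, two analysts who each follow the plan could test the same long-term claim at about 5% or about 10%.

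A reader might also infer that the ANOVA F test is badly wrong. It is not: uncorrected, it runs at 5.4-5.8%. The weakness lies in the pairwise contrasts.

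**Conclusion.** The point holds conditionally. If LSD is run with one pooled within-subject error and correlation falls with time, the between-arm difference in change from baseline to the final wave is tested at about 6-10% for a nominal 5%. On equally spaced waves with AR(1) decay, adjacent-wave changes are tested at about 2.5-4%; milder decay moves them closer to 5%. An omnibus gate corrects the long-term level only when no wave differs. After a real but faded short-term effect, the rate is about 9-10% under the correlations simulated.

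This rests on assumed correlations, equal variances, 150 per arm and alpha of 0.05. With equal correlations there is no inflation. The conservative short-term result is not universal: if baseline is less correlated with both follow-ups than they are with each other (0.5/0.7/0.5), the pooled error tests both changes from baseline at 6.8%. The contrast-specific standard error held about 5% in every setting simulated.

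**What to change.** In Specific Aim 1, replace the LSD sentence with two pre-specified between-arm contrasts: the difference in change from baseline at the 4-month follow-up and at the 12-month follow-up. Take both from a repeated measures model with unstructured covariance, so that each has its own standard error. State alpha and whether the two contrasts share it.

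If ANOVA is kept, specify separate-error contrasts for the same two comparisons and a Greenhouse-Geisser correction for the F test. The separate error is the essential part, because correcting F alone leaves pooled contrasts as they were. Fix the time origin of the follow-ups in the same edit, so that the contrasts refer to defined visits.

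The cost is SAP wording and a software option, with no change to data collection. With three waves, unstructured covariance has 3 variances + 3 covariances = 6 parameters, against 2 for compound symmetry, so four more. With 300 dyads that is a small price.

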#### Attachments

**Subject Recruitment Methods & Privacy:** Using active voice, describe plans for the identification and recruitment of subjects, including how the population will be identified, and how initial contact will be made with potential subjects by those having legitimate access to the subjects' identity and the subjects' information.

Describe the setting in which an individual will be interacting with an investigator or how and where members of the research team will

meet potential participants. If applicable, describe proposed outreach programs for recruiting women, minorities, or disparate populations as participants in clinical research. Describe steps taken to minimize undue influence in recruiting potential participants.

Please note: Based upon both legal and ethical concerns, the UK IRB does not approve finder's fees or "cold call" procedures made by research staff unknown to the potential participant.

For additional details, see topic "Recruitment of Subjects/Advertising" on ORI's [IRB Survival Handbook web page](#) and the PI Guide to Identification and Recruitment of Human Subjects for Research [\[PDF\]](#).

HF patients will be referred to this project by physicians and nurse practitioners from multiple recruitment pools: Cardiology at the Linda and Jack Gill Heart Institute, University of Kentucky Chandler Medical Center, Good Samaritan and the Chandler Medical Center Hospitals and associated University of Kentucky Clinics and Baptist Health Lexington Hospital and outpatient clinics.

In the UK facilities, a trained nurse research assistant who has background of cardiovascular nursing will screen participants for eligibility by reviewing medical charts. A trained nurse researcher will screen patients' eligibility before patients arrive by reviewing medical chart at their appointment time. Then, the UK CON nurse will contact the patient via phone and using the approved script will tell them briefly about the study and request to meet them at their appointment time to further discuss the study. When the eligible dyads are willing to participate in the study, they will sign the approved consent after they receive information on the study contents.

In the Baptist Health Lexington locations, the healthcare providers caring for cardiovascular patients will review the medical record for eligibility and then refer eligible patients to the recruiter who is a UK research assistant.

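### Aim 2 randomizes within baseline sodium strata but tests with an unstratified logrank and does not commit the Cox model to that stratum

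*Combined protocol and SAP*

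**What the plan says.** **Randomization.** Research Description, Study Design: "Dyads will be randomly assigned to intervention or usual care group using a stratified randomization strategy", once baseline adherence is known. The stated reason is that baseline adherence could influence outcomes. Research Procedures gives the same rule, and allocation comes "After patients are categorized as adherent or non- adherent using 3000mg urine sodium cut point". No other stratification factor is named. The Background adds that nonadherence to the sodium-restricted diet is among the main predictors of readmission for worsening heart failure.

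**Test.** SAP, Specific Aim 2: "Kaplan-Myer survival analysis with a logrank test will be used to make an overall comparison" of time to rehospitalization or death. No strata are named.

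**Estimate.** In the same paragraph, "Cox proportional hazards model will be used to estimate the hazard ratio of intervention effect", "while controlling potential compounding factors". None of these factors is listed, so baseline adherence is neither included nor excluded.

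**The concern.** The plan balances the arms on a factor it regards as prognostic and then does not carry that factor into the Aim 2 test. Two things follow.

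- Stratified allocation removes chance imbalance between arms on the stratum. The unstratified logrank variance still allows for that imbalance. If the stratum predicts events, the variance is too large for the design, and the test rejects less often than its nominal level. Ignoring a prognostic factor also mixes patients of unequal risk in each risk set, which dilutes the contrast between arms.
- The p-value comes from an unadjusted comparison and the hazard ratio from a model with open covariates. They may disagree, and the plan does not say which governs.

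Aim 2 may have little power to spare, as the first calculation under the working shows.

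**Working it through.** **The plan's own figure.** The only size given is 300 dyads, so 300 patients for Aim 2 (Study Population). That section points to a justification in a data analysis section that is not in the supplied text. Alpha, power, target hazard ratio, event rate and allocation ratio are not given, so 300 cannot be reproduced.

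**Reference power at assumed values** (Schoenfeld, two-sided 0.05, 1:1, D events):

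power = Φ(|ln HR| × √(D/4) − 1.96)

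- HR 0.70, D = 90: 0.357 × 4.743 − 1.96 = −0.27, power 39%.
- HR 0.70, D = 150: 0.357 × 6.124 − 1.96 = 0.22, power 59%.
- HR 0.60, D = 90: 0.511 × 4.743 − 1.96 = 0.46, power 68%.
- HR 0.60, D = 150: 0.511 × 6.124 − 1.96 = 1.17, power 88%.

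**Effect of ignoring the stratum, by simulation.**

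- From the documents: 300 patients, two arms, allocation within two sodium strata, 12 months of event follow-up.
- Assumed: 1:1 allocation; constant and proportional hazards; true hazard ratio 0.67 in both strata; 50% nonadherent (the Background says nonadherence runs as high as 50%); about 10% random censoring; 12-month event risk in adherent controls of 30% or 40%; two-sided 0.05.
- Varied: the hazard ratio of nonadherent to adherent patients.
- Statistics: unstratified U²/V, and stratified (ΣU)²/ΣV summed over the two strata, each compared with 3.84. There were 20,000 replicates, so the simulation error is about 0.35 points per power figure and less for the paired gains.

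| Stratum HR | Risk 30%: unstratified v stratified | Gain (points) | Risk 40%: unstratified v stratified | Gain (points) |
|---|---|---|---|---|
| 1 | 39.7% v 39.6% | 0.0 | 50.6% v 50.5% | −0.1 |
| 1.5 | 45.5% v 46.1% | 0.6 | 56.9% v 57.4% | 0.5 |
| 2 | 49.7% v 51.5% | 1.8 | 60.4% v 62.9% | 2.4 |
| 3 | 54.4% v 59.7% | 5.3 | 61.7% v 69.1% | 7.4 |

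With 30% or 70% nonadherent and a risk of 40%, the gains are 2.2 and 1.8 points at stratum HR 2, and 6.8 and 5.8 points at stratum HR 3. A separate run, also with 300 patients and a true hazard ratio of 0.67, gave 51% v 51%, 54% v 57% and 58% v 65% (whole points) at stratum HR 1.5, 2 and 3.

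**Under no treatment effect.** Over the two event risks, the unstratified test rejected 4.1% to 4.6% of the time at stratum HR 2 and 3.3% to 3.7% at HR 3. The stratified test rejected 4.7% to 5.2%. The departure is conservative.

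**The case against.** An unadjusted logrank test followed by an adjusted Cox model is a conventional pairing, and any such pair can disagree. The unstratified test controls type I error. The protocol says only that adherence could influence outcomes; it gives no effect on rehospitalization or death. At a stratum hazard ratio of 2 or less the gain is about 2 points or smaller. The investigators may well put baseline adherence in the Cox model. All of this stands, and it limits the weight of the point. It does not explain why a factor judged important enough to randomize on is left out of the test.

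A reader might infer three stronger things that the documents do not support.

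- *Pooling hospital and clinic recruits in one logrank test pulls the hazard ratio toward 1.* A logrank test yields no hazard ratio. The plan's hazard ratio comes from the Cox model, and it is affected only if a prognostic factor is missing from covariates the plan has not named.
- *Recruitment setting is the main stratum missed.* The referral pools do include "Good Samaritan and the Chandler Medical Center Hospitals and associated University of Kentucky Clinics and Baptist Health Lexington Hospital and outpatient clinics". But these are institutions, and the text does not say that inpatients or recently discharged patients are enrolled. University staff "request to meet them at their appointment time to further discuss the study", and usual care is that "provided at the clinics from which they were recruited". Patients reached through physician mailings or advertising may fit neither category. The hospital share and the effect of setting are not given. If half were hospital recruits, stratifying by setting would gain 1.1 to 2.0 points at a setting hazard ratio of 2 and 4.6 to 8.1 points at 3 (true hazard ratio 0.60 or 0.70).
- *The unstratified test gives false positives.* Ignoring the sodium stratum makes the test conservative. Pooling over setting, in simulations without a sodium stratum, left type I error at 4.8% to 5.0%.

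**Conclusion.** The point holds as an efficiency and consistency matter, not as a threat to validity. The Aim 2 test is not aligned with the stratified randomization, and the Cox model does not commit to the stratum. The likely cost is small: under 1 point of power at a stratum hazard ratio of 1.5, about 2 points at 2 and about 6 points at 3. Stratifying changes power by no more than about 0.1 point if the stratum is not prognostic. These figures rest on the assumed true hazard ratio of 0.67, event risks, share nonadherent, proportional hazards and a common treatment effect across strata. The direction depends only on the stratum being prognostic, which the protocol itself expects.

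**What to change.** In the SAP, Specific Aim 2:

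1. Make the test a logrank test stratified by the 3000 mg randomization stratum.
2. Estimate the hazard ratio from a Cox model stratified by the same factor. With treatment as the only covariate, and apart from ties, its score test is the stratified logrank test, so test and estimate answer one question. List any further covariates in advance and say which model governs.
3. Keep the unstratified logrank test as a sensitivity analysis.
4. Optionally, add recruitment setting as a pre-specified Cox covariate, provided it is recorded at consent and defined for every recruitment route, including mailings and advertising.

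Items 1 to 3 cost SAP wording only, because the stratum must be known for every patient before randomization. With two strata and 300 patients, the loss of information from stratifying is negligible. Item 4 needs a defined data field, which the documents do not name, and its benefit cannot be sized from them.
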